## OBJECTIVES

### Primary Objective

To determine whether there is a cerebral pain signature

### Secondary Objectives

To understand how the cerebral pain matrix, including brainstem, anterior cingulate cortex, thalamus and cerebral cortex interact with one another, and with the spinal cord and peripheral nervous system, for pain perception and its modulation.

To determine whether stimulation of the DRG, Spinal Cord, Brain, or periphery alter sympathetic nervous system activity and whether these changes (if present) are related to pain relief.

## STUDY DESIGN

This is a prospective study. Participants are chronic pain patients admitted to the John Radcliffe Hospital to receive deep brain stimulation, spinal cord stimulation, DRG stimulation, or noninvasive stimulation treatment for pain relief. Their standard clinical treatment involves two operations: stage 1 operation for deep brain or spinal electrode implantation, and stage 2 for pulse generator implantation, which is usually performed one week after stage one operation (for DBS/SCS/DRG patients). The baseline Quantitative Sensory Testing (QST), EEG, MEG, EMG, and Microneurography will take place pre-operatively, within 6 weeks post-operatively and at 6 months. LFP recording will take place between stage 1 and 2 (where appropriate). None of the tests will interfere with the patient's usual treatment.

In addition, a control cohort of healthy subjects that have not experienced chronic pain will be recruited as a comparator group to observe the cerebral signature during non-painful states.

## Summary of Study Design

Pre-operatively, before 6 weeks post-operatively and at 6 months post-operatively, patients will undergo standard Quantitative Sensory Testing (QST), EEG, MEG, EMG, microneurography and measurement of autonomic parameters (heart rate, 24 hour ambulatory blood pressure, ECG and galvanic skin response). These sessions will not last longer than 2 hours each.

Patients with externalized electrodes are expected to spend one hour a day for 2 days during their stay in the hospital or will be tested intraoperatively. We use computer-based mental tasks to distract patients from their pain, decreasing their pain perception. We record their brain, spinal or DRG electrophysiological signals - local field potentials - to analyse what happens to their nervous system when pain decreases. We will also use electrical, thermal and pressure/ pin prick stimulation on patients' limbs, producing graded painful feeling, and record and analyse their signals during the time to see what kind of signals are related to pain.

A control cohort of healthy age-matched subjects that have not experienced chronic pain will be recruited as a comparator group to observe the normal cerebral signature during unaffected by chronic pain.

## Primary and Secondary Endpoints/Outcome Measures

In the intervention group, we will observe the changes of LFPs of various cerebral, spinal and DRG nuclei induced by endogenous pain modulation, therapeutic DBS and TMS/tDCS. We will also investigate the differences of LFPs of various nuclei induced by medications.

Cortical signatures of pain will be recorded to identify global changes in neural excitation under chronic pain and therapeutic states. This will be identified using MRI, MEG/EEG recordings and Quantitative sensory testing (QST). In the intervention group, this will be undertaken during endogenous pain modulation, therapeutic DBS, SCS, DRGS and TMS/tDCS. We will also observe changes in autonomic parameters induced by stimulation.

In the control group, we will identify the brain wave patterns via MEG/EEG during quantitative sensory testing (QST), TMS/tDCS and during cognitive tasks in order to compare the chronic pain cerebral patterns with that of the healthy brain.

## STUDY PARTICIPANTS

### Overall Description of Study Participants

Patients with chronic medicine-refractory neuropathic pain that are referred to the Department of Neurological Surgery for DBS, SCS or DRG treatment, or for treatment with noninvasive electrical/radio wave stimulation. Controls will also be recruited.

#### Chronic pain patients:

##### Inclusion Criteria

Patients who are willing and able to give consent to the study.

Male or Female, aged 18 years or above.

Treatment includes DBS of ACC, PAG or sensory thalamus (VPL or VPM), SCS or DRG stimulation, or peripheral analgesic stimulation.

##### Exclusion Criteria

Patients may not enter the study if any of the following applies:

Patients who do not wish to be in the study.

Patients with extreme language barrier that cannot understand the purpose of the study despite the use of an interpreter.

*(see below for non-invasive stimulation-specific exclusion criteria)*

#### Controls:

##### Inclusion Criteria

Patients who are willing and able to give consent to the study.

Male or Female, aged 18 years or above.

##### Exclusion Criteria

Participants may not enter the study if any of the following applies:

Participants who do not wish to be in the study.

Participants with extreme language barrier that cannot understand the purpose of the study despite the use of an interpreter.

Participants with a history of neurological disorders.

Participants with a history of psychiatric disorders.

Participants who have chronic pain.

Participants who have acute pain.

Participants who had ever undergone neurosurgery.

#### Participant recruitment:

The intervention group will be recruited from neurosurgery clinics lists of patients with known DBS, spinal or DRG electrodes implanted. They will be invited to participate in the study either in

person at clinic appointments or by telephone. Participant information leaflets will be given to patients ahead of participation in the study to allow for informed consent for participation.

To recruit an appropriately age and sex-matched control group, spouses and partners of participants within the intervention group will simultaneously be invited to participate and will receive the relevant participant information sheet. Participants will also be recruited by word-of-mouth as a passive recruitment strategy. This will allow willing members of the participants' community to self-identify interest in partaking in the study. Exclusion criteria can be found above.

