## **Informed Consent**

Informed consent to this study will be obtained prior to the participants' inclusion in the study. In addition, verbal consent will also be acquired at the point of each research intervention. The patients will be supplied with Patient Information Sheets in advance of the surgery while participants will be provided with the Healthy Volunteer Information Sheet at least 2 weeks prior to involvement in any imaging or testing. Consent will be taken by the pain nurse or someone else independent of the direct care team.

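### Recruiting the intervention group from already-implanted patients conflicts with pre-surgical entry and with the pre-operative QST and autonomic baseline; the sections must be reconciled.

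*Combined protocol and SAP*

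**What the plan says.** **Recruitment source.** The Participant recruitment section states: "The intervention group will be recruited from neurosurgery clinics lists of patients with known DBS, spinal or DRG electrodes implanted". Patients are approached in clinic or by telephone. The sentence covers the whole intervention group without qualification.

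**Entry point elsewhere.** Study Design says: "Participants are chronic pain patients admitted to the John Radcliffe Hospital to receive deep brain stimulation", with the other stimulation treatments listed after it. Overall Description of Study Participants describes patients "referred to the Department of Neurological Surgery for DBS, SCS or DRG treatment". Informed Consent says: "The patients will be supplied with Patient Information Sheets in advance of the surgery". All three describe people who have not yet had the operation.

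**Schedule.** Study Design describes two operations: "stage 1 operation for deep brain or spinal electrode implantation, and stage 2 for pulse generator implantation", the second usually one week after the first. A sentence there that also covers baseline QST, EEG, MEG and EMG ends: "Microneurography will take place pre-operatively, within 6 weeks post-operatively and at 6 months". Summary of Study Design repeats this timing. Procedure (Intervention Group) and Interventions also place QST and the autonomic tests before and after surgery. Rationales behind this protocol says autonomic measures have to be taken before the intervention, and again after acute and chronic stimulation, to look for plasticity.

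**LFP window.** Study Design places LFP recording between the two stages, where appropriate. Summary of Study Design adds: "Patients with externalized electrodes are expected to spend one hour a day for 2 days during their stay in the hospital", with intraoperative testing as the alternative. The Synopsis makes cerebral LFP differences the primary endpoint.

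**The concern.** A pre-operative measurement cannot be taken prospectively in someone whose electrodes are already in place. Staff who follow the recruitment sentence literally would enrol surgical patients for whom the first of the three scheduled QST and autonomic assessments has normally passed. It cannot be recovered later.

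Two things are at stake. The first is the before/after comparison of autonomic measures on which the protocol rests its plasticity question, together with the matching QST comparison. The second, for DBS patients enrolled after the pulse generator is in, is the cerebral LFP recording that feeds the primary endpoint.

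Analysis of Outcome Measures uses all participant data unless consent is withdrawn. It gives no rule for a patient without a baseline, so the plan does not say how such a patient would enter an analysis of change.

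**Working it through.** The plan gives no figure to reproduce here. The check is a comparison of sections, followed by a count of what each entry time leaves obtainable.

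**Step 1: do the entry points agree?** Participant recruitment puts entry after implantation. Study Design, Overall Description of Study Participants and Informed Consent put it before surgery. The Participants paragraph under Experimental protocol speaks of patients who have had electrodes inserted, but that may only describe their status at the inpatient recordings, so it is weak support for late entry.

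**Step 2: is there a fallback for a missed baseline?** Procedure (Intervention Group) allows for a pre-operative MRI, and on a generous reading EEG/MEG, done before recruitment. Magnetoencephalography arranges an MRI for patients who did not have one before surgery. No visible section makes such an allowance for QST or autonomic testing.

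**Step 3: count by entry time.** For each surgical patient let P, E and M be 1 if the pre-operative, within-6-weeks and 6-month QST/autonomic visits can still be done, and 0 otherwise. Then:

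- visits = P + E + M (of 3)
- pre/post contrasts = P × (E + M) (of 2)
- early-versus-6-month contrast = E × M (of 1)

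Study Design does not say which operation *pre-operatively* refers to. Reading A is before stage 1, the natural sense of a baseline; Reading B is before stage 2.

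| Entry | P, E, M | Visits | Pre/post | Early vs 6-month | Cerebral LFP (DBS only) |
|---|---|---|---|---|---|
| Before stage 1 | 1, 1, 1 | 3 | 1 × (1 + 1) = 2 | 1 | obtainable |
| Between stages, Reading A | 0, 1, 1 | 2 | 0 × (1 + 1) = 0 | 1 | obtainable |
| Between stages, Reading B | 1, 1, 1 | 3 | 1 × (1 + 1) = 2 | 1 | obtainable |
| After stage 2, within 6 weeks | 0, 1, 1 | 2 | 0 × (1 + 1) = 0 | 1 | normally missed |
| 6 weeks to 6 months | 0, 0, 1 | 1 | 0 × (0 + 1) = 0 | 0 | normally missed |
| After 6 months | 0, 0, 0 | 0 | 0 × (0 + 0) = 0 | 0 | normally missed |

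Assumptions: post-operative time runs from implantation, and an entrant within 6 weeks can still be given the early visit inside the window. The choice of reading changes only the between-stages result, and that gap is usually one week.

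**Step 4: what does late entry leave intact?** The Synopsis lists MSNA and MEG/EEG on and off stimulation as secondary endpoints. Microneurography takes both recordings in one session, so no pre-operative visit is needed. Patient-control comparisons of QST and EEG/MEG also remain possible. SCS and DRG patients supply no cerebral LFPs whenever they enrol; a late one normally misses only the spinal or DRG recordings listed under Primary and Secondary Endpoints/Outcome Measures.

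**The case against.** The best counter-argument is that a second entry stream was intended. The Non-invasive Brain Stimulation section compares conditions in patients on SCS or DRG stimulation, who are implanted by definition. Magnetoencephalography mentions recruitment to MEG as if it were a separate step. The Amendment History says amendment 7 brought in healthy controls, pre-operative MRI and TMS/tDCS, and the recruitment section contains the control recruitment text. The sentence may have been written for that added work, in which case what is missing is a statement of scope. This is plausible and affects how the fix should be worded. It does not remove the conflict, because the sentence speaks of the intervention group as a whole and no visible section limits it.

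A second argument is that most sections agree on pre-surgical entry, so the recruitment sentence is just loose. Perhaps, but it is the sentence that tells staff whom to approach. The Appendix B patient flowchart is not shown and might show the intended entry point; it could not change the wording of the recruitment section.

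Three stronger conclusions are tempting, and the documents do not support them:

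- *Every already-implanted entrant loses all pre/post information.* Not so under Reading B for entry between stages. Early post-operative entrants also keep the early-versus-6-month comparison, which bears on the acute and chronic stimulation that the rationale mentions.
- *The primary endpoint is lost for the group.* The loss is confined to DBS patients enrolled after stage 2, and the protocol never expected LFPs from everyone.
- *The loss of power can be calculated.* The documents give no share of late entrants, no significance level and no power, and the Synopsis does not name a pre/post QST endpoint. Any figure would rest wholly on assumptions.

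**Conclusion.** The point stands as an internal inconsistency that should be fixed. For surgical patients, the stated recruitment source contradicts the pre-surgical entry point and the pre-operative QST and autonomic schedule.

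Per patient, entry after stage 2 reduces the pre/post contrasts from 2 to 0. Entry between stages does the same only if *pre-operatively* means before stage 1. For DBS patients, entry after stage 2 normally also forfeits the cerebral LFP recording. The total effect on the study cannot be sized, because the share of patients entering late is not given.

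Confidence is high on the textual conflict and lower on how much data would be lost, since late entry may be intended for the MEG and non-invasive stimulation work and the flowchart is not visible. A reader might infer that the study cannot meet its objectives. The documents do not support that: On/Off contrasts and patient-control comparisons do not depend on the baseline.

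**What to change.** 1. Reword Participant recruitment to agree with Study Design, Overall Description of Study Participants, Procedure and Informed Consent, so that surgical patients meant for the pre/post and LFP work are identified and consented before stage 1.
2. State in Study Design which of the two operations *pre-operatively* refers to.
3. If already-implanted patients are also meant to enter, for example for the MEG or non-invasive stimulation work, say so and record enrolment time relative to stages 1 and 2.
4. State in the analysis section that these patients contribute to On/Off and patient-control comparisons, and to the early-versus-6-month comparison where both visits were obtained. They do not contribute to pre/post change analyses, and they join LFP analyses only where a recording exists.

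The cost is some rewording, an earlier invitation and one extra data field. The real downside is slower accrual of patients with a baseline.

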## SYNOPSIS

Study Title	The cerebral signature for pain perception and its modulation
Study Design	Prospective study
Intervention Group	All chronic neuropathic pain patients treated with deep brain Stimulation, Spinal Cord Stimulation including targeted stimulation of the Dorsal Root Ganglion, and noninvasive neurostimulation.
Number in Intervention Group	Approximately 50 patients minimum
Control Group	Healthy volunteers with no history of chronic pain, no acute pain, no previous neurosurgery and , no neurological/psychiatric comorbidities.
Number in Control Group	Approximately 50 minimum
Planned Study Period	September 2013 to December 2019
Primary Objective	To determine whether there is cerebral pain signature
Secondary Objectives	To understand how the cerebral pain matrix, including brainstem, anterior cingulate cortex, thalamus and cerebral cortex interact with one another and with the spinal cord and dorsal root ganglia for pain perception and its modulation. Also, to determine whether stimulation has an effect on the autonomic nervous system.
Primary Endpoint	Differences of LFPs of various cerebral nuclei induced by endogenous pain modulation and DBS in chronic pain compared to healthy controls

Secondary Endpoints	Differences of LFPs of various cerebral nuclei induced by Analgesics, Difference in Muscle Sympathetic Nerve Activity (MSNA), Magnetoencephalographic (MEG) or Electroencephalographic (EEG) signals on and off stimulation and other autonomic parameters
Intervention (s)	Quantitative Sensory Testing, and patients' everyday analgesics, Micro-neurography, EMG, and LFP, EEG or MEG recording of brain or DRG, Non-invasive brain stimulation (TMS/tDCS) in chronic pain compared to healthy controls

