In addition to these questions, we would also like to investigate the effects of stimulation on the autonomic nervous system to see whether modulation of this system is responsible (at least in part) for the effects of stimulation on pain relief. We have previously shown that stimulation can alter sympathetic nerve activity but would like to investigate this further, especially looking at the peripheral part of the system (dorsal root ganglion (DRG)).

Previous unpublished data suggests that the left side of the brain may modulate pain differently than the right side. In order to ascertain these differences we would utilize the high temporal and spatial resolution of MEG to compare brain signals in various patient states.

In order to validate the clinical significance of MEG-identified signatures, we intend to recruit healthy controls for comparison of neural signatures in pain-free individuals. Furthermore, we wish to evaluate this objectively identified pain signature by localizing the brain structures involved from MRI scans and conducting non-invasive targeted inhibition of these signal with TMS/tDCS to evaluate its impact on pain relief and cognitive function.

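### Recruiting patients' partners as controls works against the sex matching it is meant to deliver, and no quota or covariate corrects it

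*Combined protocol and SAP*

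**What the plan says.** Under Participant recruitment, aim and means stand in one sentence: "To recruit an appropriately age and sex-matched control group, spouses and partners of participants within the intervention group will simultaneously be invited to participate". The same section adds word of mouth "as a passive recruitment strategy", which leaves willing people in the patients' "community to self-identify interest in partaking in the study". It sets no sex quota and no rule for choosing among volunteers.

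The control inclusion criteria admit "Male or Female, aged 18 years or above", and the control exclusion criteria do not mention sex. The Summary of Study Design promises less than the recruitment section: "A control cohort of healthy age-matched subjects that have not experienced chronic pain will be recruited", with nothing on sex. The Synopsis gives the control group size as "Approximately 50 minimum" and the same approximate minimum for patients.

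The controls have a defined purpose. The Background states: "In order to validate the clinical significance of MEG-identified signatures, we intend to recruit healthy controls". The endpoints section records MEG/EEG in controls "in order to compare the chronic pain cerebral patterns with that of the healthy brain". Analysis of Outcome Measures and Analysis of Endpoints name software and a search for differences in spectral power. They give no model, covariate, stratification or couple-level method.

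**The concern.** Inviting partners may well help with age. For sex it does the opposite of what is intended whenever the couple is of different sexes: a female patient brings a male control, and the reverse. A patient group with more women than men then tends to produce partner controls with more men than women.

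If QST thresholds or EEG/MEG power differ between men and women, part of that difference appears in the patient-control contrast and can be read as an effect of chronic pain. That contrast is the one meant to validate the MEG signature. A report could also cite the recruitment section and describe the groups as sex-matched when no step had made them so.

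**Working it through.** The documents give no figure on sex balance, so there is nothing to reproduce. Only the group sizes (about 50 and 50, Synopsis) come from the plan. All other inputs below are assumptions, shown as ranges.

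**Sex mix.** Let p be the share of women among patients, s the share of controls who are different-sex partners, and r the share of women among word-of-mouth controls.

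- Share of women among controls: c = s(1 − p) + (1 − s)r
- Gap = p − c. If r = p, the gap is s(2p − 1). If r = 0.5, it is (p − 0.5)(1 + s).
- Bias = sex effect (in SD) × gap

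The gap is zero at p = 0.5 in both cases, and same-sex couples shrink it.

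**Test.** Unadjusted two-sided two-sample t-test at 5%, 50 v 50. The standard error is √(2/50) = 0.20 SD, and the false-positive rate comes from the noncentral t distribution. Example: p = 0.7, s = 0.5, r = 0.7 gives c = 0.5 × 0.3 + 0.5 × 0.7 = 0.5 and a gap of 0.2. With a sex effect of 0.5 SD the bias is 0.10 SD, and the false-positive rate is 7.9%.

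Partners are not independent of their patients, so the same test was simulated with a within-couple correlation of 0.2 (200,000 runs per cell).

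| Control source | Women: patients → controls | Gap (points) | Sex effect (SD) | Bias (SD) | False positives, independent | False positives, correlation 0.2 |
|---|---|---|---|---|---|---|
| Half partners, rest as patients | 60% → 50% | 10 | 0.3 | 0.03 | 5.3% | 4.3% |
| | | | 0.5 | 0.05 | 5.7% | 4.8% |
| | 70% → 50% | 20 | 0.3 | 0.06 | 6.0% | 4.9% |
| | | | 0.5 | 0.10 | 7.9% | 6.9% |
| Half partners, rest 50% women | 60% → 45% | 15 | 0.3 | 0.045 | 5.6% | 4.6% |
| | | | 0.5 | 0.075 | 6.6% | 5.9% |
| | 70% → 40% | 30 | 0.3 | 0.09 | 7.3% | 6.2% |
| | | | 0.5 | 0.15 | 11.5% | 10.2% |
| All partners | 60% → 40% | 20 | 0.3 | 0.06 | 6.0% | 4.0% |
| | | | 0.5 | 0.10 | 7.9% | 6.2% |
| | 70% → 30% | 40 | 0.3 | 0.12 | 9.1% | 6.8% |
| | | | 0.5 | 0.20 | 16.8% | 14.3% |

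The all-partner rows are unlikely, given the word-of-mouth route and the health exclusions for controls. Positive correlation lowers the rates because the independent-groups test then overstates the standard error. It does not remove the bias.

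**Chance for comparison.** Two unmatched groups of 50 differ in their share of women with an SD of √(2 × 0.5 × 0.5 / 50) = 0.10, or 10 points. Chance gaps average zero; the partner gap has a fixed direction once p differs from 0.5.

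**With sex in the model.** In the same simulation the bias is zero within simulation error. At correlation 0.2 without a couple term, the test is conservative: 3.8–4.0% with half partners and 2.8–2.9% with all partners. Couple-clustered standard errors give 5.0–5.2% and 5.2–5.7%. A couple random effect fitted by REML (5,000 runs) gives 4.6–5.6%.

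**The case against.** The strongest reply is that no harm follows from the documents alone. They do not give the patients' sex ratio, so even the direction of any bias is unknown, and at 50% women it vanishes. Partners are invited, not guaranteed to enrol; word of mouth and the exclusions for pain, neurological or psychiatric history and neurosurgery all dilute the effect. In the mildest scenario the bias is 0.03–0.10 SD against a standard error of 0.20 SD. At correlation 0.2, five of the twelve error rates fall below 5%. The t-test modelled here is not in the plan, and an unspecified analysis does not exclude adjustment.

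The reach is also limited. The documents plan no LFP recording in controls, and the protocol rests cause and effect on changes within patients. Where the groups are compared on a change (on/off stimulation or task-related), a constant sex difference in level cancels, and only a sex difference in the change would matter.

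All of this stands as a limit on size and scope. It does not answer the point itself: the plan names a recruitment method as its means of sex matching, and that method mismatches sex in every different-sex couple. The protocol allows staff to choose volunteers for balance but does not require it, and adjustment that is merely possible is not prespecified. Rates below 5% reflect an overstated standard error, not an absence of bias.

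**Conclusion.** The concern holds. Partner recruitment cannot deliver the stated sex matching and, in different-sex couples, pushes the control group's sex mix away from the patients'. Nothing else in recruitment, eligibility or analysis corrects it. The recruitment section (age and sex) and the design summary (age only) also disagree on what is matched.

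The conclusion about the text is firm; the size of the consequence is not known. With half the controls partners, the assumed ranges give false-positive rates of 4.3–11.5%. The top figures, 14.3–16.8%, need all controls to be partners, 70% women among patients and a 0.5 SD sex effect together. The point is confined to the patient-control QST and EEG/MEG comparison, makes no claim about age, and should be put right before that comparison is analysed.

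**What to change.** - **Recruitment:** use word-of-mouth volunteers to frequency-match controls to the enrolled patients' distribution of sex and age. Otherwise remove the claim of sex matching. Make the design summary agree with whichever is chosen.
- **Analysis:** prespecify sex, with age as a routine companion, as covariates in the patient-control QST and EEG/MEG models.
- **Couples:** record a couple identifier. Where partners are enrolled, allow for within-couple correlation by a couple random effect or by couple-clustered standard errors with a small-sample correction. This keeps the test at its nominal level; it is separate from the sex bias.

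The cost is some wording, two covariates that are simple to record, and one identifier. Adjusting for sex multiplies the variance of the group difference by 1/(1 − R²), where R² = gap² / [4q(1 − q)] and q is the pooled share of women in two equal groups. This gives 1.0% for 60 v 50% women, 4.3% for 70 v 50%, 10.0% for 70 v 40% and 19.0% for 70 v 30%. Frequency matching reduces that cost but may mean declining some willing partners.
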